8. SAFETY

Safety will be assessed by the Data Safety Monitoring Board and events will be adjudicated for review by the Clinical Events Committee, as outlined in the NITE 1 protocol. For final analysis of the safety events, binary rates will be calculated using a denominator as the number of all subjects in the study regardless of their follow-up time.

8.1. Adverse Events

The number and percentage of patients experiencing Adverse Events will be summarized. Summary Table 6.5 entitled *Summary of Site-Reported Adverse Events by Event Type*. Results will be supported by the data presented in Listing 6.5 *Adverse Events*, sorted by patient number and the date of procedure.

8.2. Serious Adverse Events

Summary Table 6.6 entitled *Overall Summary of Serious Adverse Events* will include counts and percentages. Results will be supported by the data presented in Listing 6.6 *Serious Adverse Events*, sorted by patient number and the date of procedure.

8.2.1.1. Summary of Device-Related Serious Adverse Events

All summaries of device-related SAEs will be presented separately and for the individual events.

The number and percentage of patients experiencing device-related SAEs will be summarized. Summary Table 6.6.1 entitled *Summary of Site-Reported Device-Related Serious Adverse Events* will include counts and percentages of patients (and event counts) following the category listed below. Results will be supported by the data presented in Listing 6.6 *Serious Adverse Events*, sorted by patient number and the date of procedure.

- vascular complications including dissection
- pseudoaneurysm
- hematoma
- arteriovenous fistula
- thrombus formation
- embolization
- any vascular complication that may be attributed to the device AND requires surgical repair, surgical wound revision, or transfusion

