12.5 Relatedness

The relationship between the use of the medical device (including the medical - surgical procedure) and the occurrence of each adverse event shall be assessed and categorized by the site Investigator. During causality assessment activity, clinical judgement shall be used, and the protocol consulted. The presence of confounding factors, such as concomitant medication/treatment, the natural history of the underlying disease, other concurrent illness or risk factors shall also be considered by the Investigator. Causality assessment will also be reviewed and adjudicated by the Clinical Events Committee.

Each AE will be classified according to four different levels of causality. The Sponsor and the Investigators will use the following definitions to assess the relationship of the adverse event to the investigational medical device or procedures:

- **Not Related:** The adverse event is determined to be solely caused by the underlying disease, disorder or condition of the study patient, or attributable solely to other extraneous causes (unrelated to the device, device malfunction or procedure).
- **Possible:** the relationship with the use of the investigational device is weak but cannot be ruled out completely. Alternative causes are also possible (e.g., an underlying or concurrent illness/ clinical condition or/and an effect of another device, drug or treatment). Cases where relatedness cannot be assessed, or no information has been obtained should also be classified as possible.
- **Probable:** the relationship with the use of the investigational device seems relevant and/or the event cannot be reasonably explained by another cause, but additional information may be obtained.
- **Causal / Related:** The adverse event is clearly caused by the use of the device, device malfunction or the procedure, as confirmed by: the event is recognized as a known event associated with the device or procedure, the event has a temporal relationship to device or procedure, the event involves the body site or organ the device or procedure is applied to or has an effect on, or event is related error in use.

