2. INTRODUCTION

The purpose of this Statistical Analysis Plan (SAP) is to prospectively outline the methods for analyses for patients with acute ischemic stroke in the anterior circulation due to large vessel occlusion (LVO) who underwent endovascular treatment using the transcarotid approach with flow reversal in this initial feasibility (NITE 1) study using the NOVIS Neuroprotection System (NPS).

The NITE 1 study is a prospective, multi-center, single arm feasibility study for the endovascular treatment of patients with acute ischemic anterior circulation strokes due to large vessel embolic occlusions using the transcarotid approach with flow reversal. Patients enrolled into the NITE 1 study will have failed transfemoral therapy and will be followed immediately from post-op to 90 days. The primary study objective is to establish the feasibility and safety of the NOVIS NPS in the targeted study population, and as such, this SAP will focus on confirming whether the initial safety signal exists from the primary endpoint data.

With FDA's IDE approval of the study design and sample size, the primary safety study endpoints will be numerically compared to existing TCAR data from the ENROUTE NPS clinical program (PROOF and ROADSTER). The functional independence at 90 days will be compared to reference data for acute ischemic stroke (AIS) patients treated with mechanical thrombectomy and the natural history of AIS in those patients who have not received or have failed mechanical thrombectomy, as cited in Section 5. The primary study endpoints for the NITE 1 study include:

- Device-related Serious Adverse Events – vascular complications including dissection, pseudoaneurysm, hematoma, arteriovenous fistula, thrombus formation, embolization and any vascular complication that may be attributed to the device AND requires surgical repair, surgical wound revision, transfusion, etc.
- Other Serious Adverse Events – permanent cranial nerve injury (CNI), new symptomatic intracranial hemorrhage (SICH) and dissections related to ancillary devices
- Functional independence at 90 days (proportion with mRS score 0-2)

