As listed above, the first data review will compare the incidence of the device-related SAEs from NITE 1 to the device-related SAEs collected across the body of TCAR evidence to date. This comparison group will include device-related SAEs from the ENROUTE NPS clinical program (e.g., PROOF and ROADSTER) representing a patient population spanning from feasibility to pivotal to post-market study settings. In addition, the incidence of permanent CNI and new SICH from the NITE 1 patient population will be compared to the same comparison group as well as reference data for AIS patients treated with mechanical thrombectomy and the natural history of AIS in those patients who have not received or have failed mechanical thrombectomy. The use of ENROUTE NPS clinical program data as a point of comparison for device-related SAEs and permanent CNI is based on the comparability of ENROUTE NPS and NOVIS NPS. Although each device is used for different patient populations, the surgical approach and set-up of each NPS device are equivalent. In regard to new symptomatic hemorrhage, the risk for this event can be attributed to two main causes: the risk due to cerebral reperfusion injury and the risk due to interventional or mechanical manipulation of the cerebral vasculature. The first applies to both ENROUTE NPS and NOVIS NPS, since any carotid revascularization comes with risk for cerebral reperfusion injury. The latter may be considered more specific to the AIS patient population. However, due to the increased risk for bleeding among patients treated with ENROUTE NPS due to required use of DAPT pre-procedure and systemic heparinization during the procedure to achieve an ACT of > 250, which is not applicable in the NOVIS NPS procedure for AIS patients, these risks can be considered to offset one another in each population. Therefore, the occurrence for SICH from ENROUTE NPS procedures can be compared to NOVIS NPS. Next, the incidence of dissections related to ancillary devices will be compared to the dissections related to the ancillary devices used commercially for ENROUTE and captured through post-market surveillance data. These numerical comparisons are summarized below with reference to the outcome, comparison group. Finally, the functional modified Rankin Score (mRS) at 90 days will be compared to the average functional independence score at 90 days (mRS 0-2) from the relevant studies included in the meta-analysis by Mokin M, et al in AIS patients treated with mechanical thrombectomy and the natural history of AIS in those patients who have not received or have failed mechanical thrombectomy. These data comparisons are summarized in Table 1 below:

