7.4. Summary of Revascularization Success

Revascularization Success is defined as an mTICI of ≥ 2 as assessed by the angiographic core lab. Results will be tabulated using counts and percentages and presented in Table 6.4.3 entitled *Summary of Revascularization Success*. Results will be supported by the data presented in Listing 6.4.3 titled *Angiographic Core Lab Adjudication of Postprocedural mTICI*, sorted by patient number and the date of procedure.

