8.3. CEC Adjudicated Adverse Events

The number and percentage of events adjudicated by the CEC will be summarized. Summary Table 6.7 entitled *Summary Adverse Events Adjudicated by the CEC*. Listing 6.7 entitled *CEC Adjudications* supports Table 6.7.

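### SAP 8.2.1.1 plans the per-patient device-related SAE rate only as a site-reported table, and no passage says that CEC adjudication defines this primary rate

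*SAP*

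**What the plan says.** SAP 8.2.1.1 puts the number and percentage of patients with device-related SAEs in Table 6.6.1, titled "Summary of Site-Reported Device-Related Serious Adverse Events". The supporting listing is 6.6, the general SAE listing.

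Protocol 12.5 has causality "shall be assessed and categorized by the site Investigator" and adds that the CEC will review and adjudicate it. Protocol 13.2 gives the CEC all potential endpoint events and their relationship to the device or procedure, and leaves its policies and procedures to a charter. SAP 8 says that "events will be adjudicated for review by the Clinical Events Committee, as outlined in the NITE 1 protocol" and that, for the final analysis, "binary rates will be calculated using a denominator as the number of all subjects in the study regardless of their follow-up time". SAP 8.3 then describes the CEC output: "The number and percentage of events adjudicated by the CEC will be summarized" (Table 6.7, Listing 6.7).

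On the comparison, SAP 2 says that "the primary safety study endpoints will be numerically compared to existing TCAR data". SAP 5 plans to "compare the incidence of the device-related SAEs from NITE 1 to the device-related SAEs collected across the body of TCAR evidence". Neither says whether the NITE 1 side is the site or the adjudicated figure.

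**The concern.** Device attribution sets the numerator of this endpoint. If the SAP is programmed as written, the per-patient figure carries the site investigator's attribution, made in a single-arm study with the device known. The adjudicated figure does not appear per patient, by endpoint category or by device-relatedness, although the adjudication is already planned. Protocol 14.3 sets no hypothesis test, so the reported rate and its numerical comparison are the whole safety result for this endpoint. Its source should therefore be fixed before the data are seen.

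A second ambiguity bears on the same numerator. The causality scale has four levels, and the documents do not say which of them make an event device-related. Adjudication alone does not settle this, because the CEC would meet the same wording.

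**Working it through.** **1. Planned outputs side by side.**

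| Output | Content | Unit stated | Source named |
|---|---|---|---|
| Table 6.6, Listing 6.6 (SAP 8.2) | SAEs overall | counts and percentages | none |
| Table 6.6.1, Listing 6.6 (SAP 8.2.1.1) | device-related SAEs by category | patients, plus event counts | site report, in the title |
| Table 6.6.2 (SAP 8.2.1.2) | the other primary SAEs | patients, plus event counts | none |
| Table 6.7, Listing 6.7 (SAP 8.3) | events adjudicated by the CEC | events | CEC |

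Table 6.6.1 is the only row that gives device-related SAEs per patient, and its title names the site. The CEC row counts events, with no stated split by endpoint category or relatedness. By contrast, SAP 7.4 names the independent assessor in the definition of revascularization success: "as assessed by the angiographic core lab".

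**2. Is there a precedence rule?** Protocol 12.5, Protocol 13.2 and SAP 8 establish that adjudication takes place. None says that the CEC result replaces the site result in the device-related SAE rate. SAP 2, SAP 5 and SAP Table 1 name the comparator but not the source of the NITE 1 figure.

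**3. Causality wording.** The scale in Protocol 12 and 12.5 runs from not related through possible and probable to causal.
- Protocol 7.1 and SAP 8.2.1.1 use permissive wording (attribution to the device is conceivable). Read inclusively, this would count possible, probable and causal.
- Protocol Appendix 4 requires direct causation by the study device. Read narrowly, this would count causal only.

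The difference matters because Protocol 12.5 puts events whose relatedness cannot be assessed into the possible level. The inclusive reading counts them and the narrow one does not.

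**4. Size.** Inputs: the denominator is all subjects (SAP 8), which I take to mean all subjects in the population being analysed. The per-protocol minimum is 30 and maximum 40, and the intent-to-treat maximum is 60 (Protocol 14.2). If k patients are classified differently, the rate moves by k/n.

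| n | k = 1 | k = 2 |
|---|---|---|
| 30 | 1/30 = 3.3 points | 2/30 = 6.7 points |
| 40 | 1/40 = 2.5 points | 2/40 = 5.0 points |
| 60 | 1/60 = 1.7 points | 2/60 = 3.3 points |

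The shift can go either way, since adjudication may add or remove a device-related event.

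**5. What cannot be computed.** The documents give no rate of site-CEC disagreement and no device-related SAE rate for the ENROUTE program. The plan has no figure of its own to reproduce on this point.

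**The case against.** The strongest reply is that the documents already lean toward the CEC. SAP 8 is the parent of 8.2.1.1. It says events are adjudicated, and its next sentence turns to the final analysis of safety events. The natural reading is that adjudicated events feed the rates. On this view the table title only records where the report came from, as in Table 6.5, and the SAP never labels Table 6.6.1 the primary safety table. The CEC charter, which was not available for this review, may also set precedence and the causality cut. This stands in part. It rules out the stronger inference that the SAP sets adjudication aside or chooses site attribution as the governing source. It does not supply the missing sentence, and the only per-patient table still carries the site label.

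On causality, a reader might infer that device-related is undefined. That goes too far. Appendix 4 defines it, and its wording is close to the top level of the scale. The permissive phrase can also be read as qualifying only the final catch-all, which SAP 8.2.1.1 lists as a separate item. What remains is a conflict of wording and no stated mapping to the levels.

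On harm, both the site and CEC outputs are pre-specified, so neither can be dropped. A shift of 1/n is also common to any binary endpoint, and sampling error is larger: the exact 95% interval for 0/30 is 0 to 11.6%. All of this holds and limits the point to the definition of a descriptive rate. It does not make the choice of source unimportant, because a wide interval around an ill-defined rate does not cure the definition.

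**Conclusion.** The point holds and should be fixed, within limits. The per-patient rate of the first primary endpoint is planned only in a site-labelled table. SAP 8 suggests but does not state that CEC findings define the rate, and the qualifying causality levels are not named. Each patient classified differently is worth 3.3 points at n=30, 2.5 at n=40 and 1.7 at n=60, with unknown direction. Error rates are not affected, because nothing is tested.

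Two further inferences are not supported. A reader might conclude that one reclassified patient would reverse the TCAR comparison, for example by setting 3.3 points against ROADSTER's 1.8% serious dissection rate (4/219, Protocol 3.2.2). That rate covers one component event and is not the comparator. A reader might also expect the CEC to rule on seriousness. Protocol 12.5 and 13.2 give it endpoint events and relatedness, and do not mention seriousness.

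The conclusion rests on the protocol and SAP alone. If the CEC charter already sets precedence and a causality cut, what remains is to cite it and add the per-patient table.

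**What to change.** - In SAP 8.2.1.1, state that CEC-adjudicated endpoint status and device-relatedness define the device-related SAE rate and the figure compared with TCAR.
- Add a per-patient CEC-adjudicated table in the categories of Table 6.6.1, for both the intent-to-treat and per-protocol populations. Keep the site-reported table as supportive.
- Reconcile the endpoint wording with Protocol Appendix 4 by naming which of the four causality levels count as device-related, or cite the CEC charter if it already does so.
- Optional: a listing of site-CEC disagreements, and a sentence on how the ENROUTE events were attributed.

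The required changes cost a few sentences of SAP text and one more table. The adjudication of endpoint events and relatedness is already planned. The downside is that final tables must wait for adjudication to finish.

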8.2.1.2. Summaries of Other SAEs

All summaries of other SAEs will be presented separately and for the individual events:

- Permanent CNI
- New SICH
- Dissections related to ancillary devices

The number and percentage of patients experiencing other SAEs will be summarized. Summary Table 6.6.2 entitled *Summary of Other Serious Adverse Events* will include counts and percentages of patients (and event counts) following the category listed above.

8.3. CEC Adjudicated Adverse Events

The number and percentage of events adjudicated by the CEC will be summarized. Summary Table 6.7 entitled *Summary Adverse Events Adjudicated by the CEC*. Listing 6.7 entitled *CEC Adjudications* supports Table 6.7.

9. NEUROLOGICAL EVALUATIONS

9.1.1.1. Summary of Functional Independence at 90 Days

The summary of functional independence at 90 days is defined as the proportion of NITE 1 patients with mRS score 0-2 at 90 days and will be presented in Table 6.8 entitled *Summary of Functional Independence at 90 days*. Listing 6.8 entitled *Modified Rankin Scale (mRS)* supports Table 6.8.

9.1.1.2. Summary of Neurologic Assessment at 90 days

The summary of neurological assessments at 90 days is defined as the proportion of NITE 1 patients with a nondisabling or disabling stroke according to the NIHSS and will be presented in Table 6.9 entitled *Summary of Neurological Assessment at 90 days*. An NIHSS of ≤ 4 is indicative of a nondisabling stroke and an NIHSS ≥ 5 will be evaluated as a disabling stroke. Listing 6.9 entitled *NIH Stroke Scales (NIHSS)* supports Table 6.9.

